1. LIST OF ABBREVIATIONS AND DEFINITIONS OF TERMS

Term	Definition
ADR	Adverse Drug Reaction
AE	Adverse Event
CS	Clinically Significant
eCRF	Electronic Case Report Form
EOS	End of Study
EOT	End of Treatment
ES ADL	England & Schwab Activity Of Daily Living
FAS	Full Analysis Set
FSH	Follicle Stimulating Hormone
hCG	human Chorionic Gonadotropin
IP	Investigational Product
K-FAB	Korean Frontal Assessment Battery
K-MMSE	Korean Mini-Mental State Examination
LSM	Least Squares Mean
MedDRA	Medical Dictionary for Regulatory Activities
MMRM	Mixed-Effect Model Repeated Measure
MoCA-K	Montreal Cognitive Assessment-Korean Version
NCS	Not Clinically Significant
PPS	Per-Protocol Set
PSP	Progressive Supranuclear Palsy
PSP-p	Progressive Supranuclear Palsy-parkinsonism
PSP-RS	Progressive Supranuclear Palsy-Richardson's Syndrome
PT	Preferred Term
SADR	Serious Adverse Drug Reaction
SAE	Serious Adverse Event
SAP	Statistical Analysis Plan
SOC	System Organ Class
TEAE	Treatment-Emergent Adverse Event

2. INTRODUCTION

This document describes the statistical analysis plan for protocol GV1001-PSP-CL2-011. The details of the data processing and analysis methods used for statistical analysis have been described, and demographic information, efficacy and safety data will be summarized and analyzed according to the methods in this statistical analysis plan.

3. SUMMARY OF KEY PROTOCOL INFORMATION

3.1 Study Objective

3.1.1 Primary Objective

To explore the efficacy and evaluate the safety of GV1001 0.56 mg/day or 1.12 mg/day administered for 24 weeks on the severity of disease in patients with progressive supranuclear palsy.

3.1.2 Secondary Objective

To collect source data to determine the possibility of progression to the next stage of development and to subsequent clinical studies by analyzing the clinical and biological parameters associated with the treatment response and safety information of 2 dose levels of GV1001, 0.56 mg/day or 1.12 mg/day, in patients with progressive supranuclear palsy.

3.2 Study Design

This is a 24-week, multicenter, randomized, double-blind, placebo-controlled, parallel design, prospective, Phase 2a exploratory clinical study.

If the subject and/or the subject's representative provide a written consent to participate in this clinical study, the required examinations and tests will be performed at the screening visit, and the screening period will run for 4 weeks or shorter.

Subjects who are ultimately determined as eligible by the inclusion/exclusion criteria after screening will be randomized at a 1:1:1 ratio to Study Group 1 (GV1001 0.56 mg/day), Study Group 2 (GV1001 1.12 mg/day), or the placebo group depending on the study site in which they are enrolled. Depending on the randomization results, subjects will be administered the investigational product (study drug or placebo) once weekly for the first 4 weeks (1 month), and then administered 10 times at 2-week intervals for 20 weeks (5 months) for a total of 14 doses over 24 weeks (6 months).

All subjects will visit the study site according to the planned clinical study schedule to receive the investigational product and to be evaluated for efficacy and safety. To ensure the objectivity and accuracy of the study results, the efficacy evaluators evaluating the PSP-rating scale will be limited to neurologists who have been sufficiently educated and trained, and the collection of efficacy and safety evaluation data and biomarkers will be performed in a consistent order at each visit.

※ Neurological drugs administered at a stable dose for at least 1 month prior to a subject's participation in this clinical study (prior to screening) will be continued without changing the dose during the clinical study participation period.

[figure not shown]

Figure. Clinical Study Schematic

3.3 Determination of the Sample Size

Total number of subjects: 75 subjects (75 subjects in total with 25 subjects per group considering a dropout rate of 20%)

	Study Group 1	Study Group 2	Control Group	Total Number of Subjects
Number of Subjects	20	20	20	60
Number of Subjects Considering Dropout (20%)	25	25	25	75

This is a Phase 2a exploratory clinical study conducted for the purposes of collecting initial safety and efficacy information on the investigational product GV1001 in patients with progressive supranuclear palsy as well as providing the basis for design, evaluation items, and evaluation methods for subsequent clinical studies. Since this is a study to estimate the clinically significant effect size to demonstrate the efficacy of this investigational product, the number of subjects was not calculated based on statistical considerations. The minimum number of subjects required in a pilot study is 12 subjects²⁾ and approximately 30 subjects can be considered according to the rule of thumb^{3), 4)}. Therefore, by combining these, it is intended to set 20 subjects per group, and a total of 75 subjects with 25 subjects per group will be enrolled considering a dropout rate of 20%.

3.4 Schedule of Study

Period	Screening	Double blind treatment phase												Follow Up		
		1	2	3	4	6	8	10	12	14	16	18	20	22	24	26
Week	~ -4															
Visit	1	2	3	4	5	6	7	8	9	10	11	12	13	14	15	16
Visit window (days)	-	-	-	-	-	-	-	-	-	-	-	-	-	-	-	-
Subject Consent and Assignment of Screening Number																± 5
Demographic Information																
Checking Medical/Surgical History																
Checking prior/concomitant medications																
Physical examination																
Vital signs																
Weight																
Height																
Electrocardiography ^[1]																
Laboratory tests ^[2]																
Urine hCG ^[3]																
Checking inclusion/exclusion criteria																

Period	Screening	Double blind treatment phase												Follow Up			
		1	2	3	4	6	8	10	12	14	16	18	20	22	24	26	28
Week	~ -4																
Visit	1	2	3	4	5	6	7	8	9	10	11	12	13	14	15	16	17
Visit window (days)	-	-	-	-	-	-	-	-	-	-	-	-	-	-	EOT	EOS	
																	±5
Randomization	○																
K-MMSE ^[4]	○																
PSP-rating scale	○																○
MoCA-K	○																○
K-FAB	○																○
ES ADL	○																○
Brain CT ^[5]	(○)																
Collecting human-derived samples ^[6]	DNA, Plasma, Serum	○															○
	Cerebrospinal fluid	○															○
Investigational product administration ^[7]		○	○	○	○	○	○	○	○	○	○	○	○	○	○	○	
Adverse Event Assessment ^[8]		○	○	○	○	○	○	○	○	○	○	○	○	○	○	○	

[1] Electrocardiography: For the Visit 1 (screening) test, the results of a test performed within 3 months may be used if available, and retesting may be performed only once at the discretion of the investigator.
 [2] Laboratory tests: For the Visit 1 (screening) tests, the results of tests performed within 4 weeks may be used if available, and retesting may be performed only once at the discretion of the investigator. At Visit 1 (screening), the serum FSH tests shall be performed to confirm menopause in women aged ≥41 years who have experienced amenorrhea for more than 1 year.
 • Hematology test: WBC, RBC, Hemoglobin, Hematocrit, Platelets count, WBC differential count (Neutrophils, Lymphocytes, Monocytes, Eosinophils, Basophils)
 • Blood chemistry test: BUN, Creatinine, Uric acid, Total bilirubin, Albumin, Total Protein, ALT, AST, γ-GTP, Alkaline phosphatase, Glucose, Total Cholesterol, HbA1c (performed only at screening visit)

- Serum Follicle Stimulating Hormone test: FSH (Performed only at screening visit for those who require confirmation of menopause)
- Urinalysis: Protein (Albumin), Glucose, Ketones, WBC, Blood (RBC)
- Blood coagulation test: INR (performed only at screening visit)
- Thyroid test: TSH, free T4 (performed only at screening visit)
- Syphilis, AIDS tests: VDRL or RPR, anti-HIV (performed only at screening visit)
- Serum creatinine clearance will be confirmed using the Cockcroft-Gault formula. (performed only at screening visit)
$$ClCr = [(140 - \text{Age (years)}) \times \text{Weight (kg)} \times 0.85 \text{ (for female subjects)}] / 72 \times \text{Serum Creatinine (mg/dl)}$$
- [3] Urine hCG: Urine hCG pregnancy tests will be performed only for women of childbearing potential, excluding subjects confirmed to have undergone surgical sterilization and as being menopausal. However, for Visit 1 (screening), the subjects who performed the serum FSH test to confirm menopause when participating in the clinical study will also perform urine hCG pregnancy test.
- [4] K-MMSE: The results of a test performed at the study site within 2 weeks prior to the screening visit may be used if available.
- [5] Brain CT: This will be performed only on subjects without brain CT imaging within 12 months prior to the screening visit.
- [6] Collecting human-derived samples: Human-derived samples (DNA, plasma, serum, and cerebrospinal fluid) will be collected for exploratory evaluations, and they will be transferred to the central lab for analysis and storage. However, in the case of cerebrospinal fluid, it will be collected only from subjects who have separately consented to collection of samples. For Visit 1 (screening), separate visits for collecting human-derived samples can be set up and implemented within the screening period.
- [7] Investigational product administration: Subjects will be observed for approximately 20 minutes after the administration of the investigational product from Visit 2 to Visit 15.
- [8] Adverse events assessment: Adverse events that occurred after the first administration of the investigational product will be identified, and prior to the first administration, it will be collected as medical history.

3.5 Changes to Analysis from Protocol

Protocol Language	SAP Language Changed from Protocol	Reason of Change				
none	9.2.7 Change from the baseline in the total score of modified PSP-rating scale 10 after 12 weeks (3 months) and 24 weeks (6 months) of investigational product administration (...)	Add extra secondary efficacy endpoint for further exploration of efficacy				
none	9.2.8 Change from the baseline in the total score of modified PSP-rating scale 14 after 12 weeks (3 months) and 24 weeks (6 months) of investigational product administration (...)	Add extra secondary efficacy endpoint for further exploration of efficacy				
none	9.2.9 Proportion of subjects with change from the baseline in the total score of PSP-rating scale ≤ 0 after 24 weeks (6 months) of investigational product administration [Subgroup: Richardson type] (...)	Add extra secondary efficacy endpoint for further exploration of efficacy				
none	9.2.10 Proportion of subjects with change from the baseline in the total score of Modified PSP-rating scale 10 ≤ 0 after 24 weeks (6 months) of investigational product administration [Subgroup: Richardson type] (...)	Add extra secondary efficacy endpoint for further exploration of efficacy				
none	9.2.11 Proportion of subjects with change from the baseline in the total score of Modified PSP-rating scale 14 ≤ 0 after 24 weeks (6 months) of investigational product administration [Subgroup: Richardson type] (...)	Add extra secondary efficacy endpoint for further exploration of efficacy				
11.2.6. Subgroup Analysis Subgroup analysis will not be considered in this clinical study.	
11. SUBGROUP ANALYSES Subgroup analyses for efficacy will be conducted on the endpoint related with PSP-rating scale, modified PSP-rating scale 10 and modified PSP-rating scale 14 for FAS using the same analysis methods (refer to 9.1 and 9.2).
 
  
 Subgroup Variable	Category	
   
 PSP Type	 
 Richardson type [PSP-RS] Parkinsonian type [PSP-p] 	
  
	Subgroup Variable	Category	PSP Type	
 Richardson type [PSP-RS] Parkinsonian type [PSP-p] 	Add subgroup analysis for further exploration of efficacy
Subgroup Variable	Category					
PSP Type	
 Richardson type [PSP-RS] Parkinsonian type [PSP-p] 					

4. PLANNED ANALYSIS

4.1 Interim Analysis

No interim analysis will be performed before the end of the clinical study. However, an interim analysis related to the safety of this clinical study may be conducted when a serious issue related to safety is discovered and the need is recognized through a meeting or a deliberation of the investigator or principal investigator.

4.2 Final Analysis

The planned final analysis is performed after sequentially completing the following steps.

1. All subjects in the study will complete the visit defined in the protocol (LPO, Last Patient Out) and all data problems will be resolved through query.
2. The database is locked after the analysis set definition is confirmed via blind meeting and email communication.
3. Unblinding process will be conducted.

5. GENERAL CONSIDERATIONS FOR SUMMARIES AND ANALYSES

5.1 Significance Level

Unless otherwise specified, all statistical tests will be two-sided hypothesis tests performed at the 5% level of significance and all confidence intervals will be two-sided 95% confidence intervals.

5.2 Statistical Analysis Methods

For continuous data, the normality test will determine the parametric or nonparametric methods by the p-value of Shapiro-Wilk test (reference to section 14.1) with the 5% level of significance. Unless otherwise specified, the two-sample t-test (if normality assumption is satisfied) or Wilcoxon's rank-sum test (if normality assumption is not satisfied) will be used to compare each study group with the control group (GV1001 0.56 mg/day vs. control group, GV1001 1.12 mg/day vs. control group). For a within-group comparison, the paired t-test if the assumption of normality is satisfied or Wilcoxon's signed rank test if the assumption of normality is not satisfied, will be used.

For a between-group comparison of categorical data, a chi-square test will be basically used and when more than 20% of the table cells have expected frequencies that are less than 5, Fisher's exact test will be presented. A between-group comparison will be used to compare each study group with the control group (GV1001 0.56 mg/day vs. control group, GV1001 1.12 mg/day vs. control group). For confidence intervals of proportion of categorical data, if more than 20% of the table cells in the contingency tables for between-group comparison have expected frequencies that are less than 5, then exact two-sided 95% confidence intervals (Clopper-Pearson) will be calculated.

5.3 Stratifications

Not Planned

5.4 General Reporting Conventions

5.4.1 Summary Statistics

- Continuous data: Summary statistics will be presented with the number of subject(n), mean, standard deviation (SD), median, minimum (min), and maximum (max).

- Categorical data: Summary statistics will be presented with frequencies (n) and percent (%).
- When the statistics or p-value etc. are not calculated, It is presented as '-'.

5.4.2 Decimals

- Decimal place and presented down to 2nd decimal place.
- Categorical data: Percentage will be rounded up from the 3rd decimal place and presented down to 2nd decimal place.
- P-value
 - P-values will be reported to 4th decimal place.
 - If the calculated p-value is below 0.0001, it will be presented as '<0.0001'.
- Vital signs, ECG and laboratory test

Results for vital signs and ECG will be showed 1 more digit from maximum decimal places for each item, and results for clinical laboratory tests will be showed 1 more digit from maximum decimal places of the standard unit conversion value for each item.

For example, in laboratory tests, if the longest decimal place of original unit's measured value is 2 decimal places and conversion factor is 1 decimal place (i.e. the longest decimal place of standard unit's measured value is 3 decimal places), the statistic is rounded off from the 5 decimal places to 4 decimal places.

5.5 Reference Start Date and Study Day

The study day of an event is defined as the relative day of event starting from the date of randomization (reference date, Visit 2). The study day to an event cannot be 0.

- The study day of events occurring before the randomization will be calculated as:
Study Day (days) = (Date of event – Date of Randomization)
- The study day of events occurring on or after the first randomization will be calculated as:
Study Day (days) = (Date of event – Date of Randomization) + 1

Study days will only be calculated for events with completed start dates and will not be calculated for events if the start date of event is not completed.

5.6 Baseline Definition

Unless otherwise specified, Baseline is defined as the last observed value without missing prior to the first IP administration.

5.7 Medical Dictionary and Version

The Medical Coding Name and Version applied to this study are as follows.

- Medical History and Adverse Events: Medical Dictionary for Regulatory Activities (MedDRA) 26.1 or latest version
- Prior Medication/Concomitant Medication: WHO Drug Global 2023 or latest version

5.8 Software Version

SAS® (version 9.4 or higher, Enterprise BI Server, SAS institute Inc., Cary, NC, USA).

6. DATA HANDLING CONVENTIONS

6.1 Handling of Missing Data

When analyzing the efficacy endpoints and exploratory endpoints, in the case of utilizing the mixed-effect model repeated measure (MMRM) method, the available data will be analyzed as they are since the method does not require the replacement of missing values. If missing values occur in the safety endpoints and exploratory endpoints analyzed by methods other than MMRM, analysis will be performed only on the collected data without imputation.

In the PSP-rating scale, if an item has no response, the available items with responses will be used to calculate the total score and the score for each domain. The calculated scores will be converted to the same scale as the total score and the score for each domain if all items are not missing. In modified PSP-rating scale, if there is a non-response for each item, the total score and the corresponding score for each domain will be considered as missing.

6.2 Windowing Conventions

The results of efficacy assessments performed after randomization in this study will include not only regular visits, but also early termination/withdrawal visits and unscheduled visits, and measurements from the visit within the visit window will be used for the analysis.

Visit	Actual Point	Visit Window	Analysis Window Valid Relative Range*
Visit 1 (Screening)	~ - 4 Week	-	
Visit 2 (Baseline)	Week 1	-	1
Visit 3	Week 2	± 3 Days	5~11 days
Visit 4	Week 3	± 3 Days	12~18 days
Visit 5	Week 4	± 3 Days	19~25 days
Visit 6	Week 6	± 5 Days	31~41 days
Visit 7	Week 8	± 5 Days	45~55 days
Visit 8	Week 10	± 5 Days	59~69 days

Visit	Actual Point	Visit Window	Analysis Window Valid Relative Range*
Visit 9	Week 12	± 5 Days	73~83 days
Visit 10	Week 14	± 5 Days	87~97 days
Visit 11	Week 16	± 5 Days	101~111 days
Visit 12	Week 18	± 5 Days	115~125 days
Visit 13	Week 20	± 5 Days	129~139 days
Visit 14	Week 22	± 5 Days	143~153 days
Visit 15 (EOT)	Week 24	± 5 Days	157~167 days
Visit 16	Week 26	± 5 Days	171~181 days
Visit 17 (EOS)	Week 28	± 5 Days	185~195 days

* If a violation of the drug administration schedule occurs, the analysis window will be modified as the process in the protocol 5.5.2.

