6.3 Early Termination and Withdrawal Assessments

Data collected from early termination/withdrawal visits apply to the analysis as follows.

- Efficacy endpoints
 - In accordance with section 6.2, analysis is performed as result of a regular visit only when it comes within the visit window corresponding to each regular visit.
- Safety endpoints
 - It is excluded from the analysis of regular visits but will be presented in the listing.
 - If early termination/withdrawal visit is the last visit, the result value will be summarized as final visit.

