7.3 Full Analysis Set (FAS)

This includes subjects who received at least 1 dose of the investigational product after randomization and had at least 1 evaluation with the PSP-rating scale after the administration of the investigational product and up to the end of the clinical study. In the FAS, subjects will be included in the group to which they were randomized.

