5.5.2. Dropout Criteria

The following are the cases in which the subjects may request to discontinue the clinical study, or in which they may be discontinued or dropped out according to a discussion between the investigator and the sponsor.

- ① The subject or the subject's representative has withdrawn consent to participate in the clinical study.

- ② Violation of the inclusion/exclusion criteria is found during the clinical study.
- ③ Continuation of the clinical study is difficult because of adverse events or serious adverse events.
- ④ There are issues in administering the investigational product to the subject.
- ⑤ The subject is lost to follow up.
- ⑥ The subject has taken a prohibited concomitant medication, or it is determined necessary to administer a prohibited concomitant medication.
- ⑦ The subject has become pregnant during the clinical study.
- ⑧ Other cases in which the sponsor or the investigator determines that conducting the clinical study is not appropriate

For other matters related to the administration schedule of the investigational product, whether to drop out a subject will be determined based on the criteria described below.

A violation of the drug administration schedule will be treated as a minor protocol violation up to 5 times, and it will not be a condition for dropping out a subject within this limit. However, if it exceeds 5 times, the subject will be dropped out. The administration window of the drug for the first 4 weeks will be ± 3 days (however, excluding Visit 2), and thereafter, the window will be ± 5 days for the biweekly administration days. If the window of the administration day is exceeded, it will be treated and recorded as a minor violation. If the window has passed, the corresponding drug administration will be skipped and an injection will be given at the next administration day that was originally scheduled. If an injection is given before reaching the window of the administration day (e.g., at -6 days), the schedule will be adjusted by moving all subsequent administration days forward by one week. If the subject arrives at the visit day for the PSP-rating scale evaluation without 12 hours of off-medication for oral drugs that are being taken, the evaluation will be performed in that state, but it will be recorded as a minor protocol violation. However, the off-medication evaluation rules shall be followed for the remaining visit days.

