5.5.3. Protocol Violations

The principal investigator and staff members of this clinical study shall fully understand and thoroughly implement the protocol to prevent violations of the protocol. To comply with the administration and test schedule of the investigational product in this clinical study, the site staff shall provide written notifications or make telephone calls regarding the study site visit schedule to allow the subjects to make visits on the applicable days without omission. However, protocol violations that occur unavoidably will be handled as shown below.

In the case of major protocol violations, the corresponding subject will be dropped out from the analysis (excluded from the per-protocol set) as a rule, and the applicable situations are as follows:

- ① Informed consent form was not obtained.
- ② The inclusion/exclusion criteria were violated.
- ③ Prohibited concomitant medications were administered during the clinical study.
- ④ The PSP-rating scale test of Visit 1 (screening), which is the first visit of this study, and Visit 16 (Week 26) were missed.

Other minor protocol violations that are judged as having no impact on the interpretation of the clinical study results will be included in the per-protocol set analysis by accurately describing the extent of violation or delay and the reason, and comprehensively considering whether the clinical study has been affected through a blind meeting prior to database lock.

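### The ±5-day analysis windows in SAP 6.2 leave three-day gaps around Visits 10 and 16, so an observed rating that is 6 to 8 days off target is assigned to no visit

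*SAP*

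**What the plan says.** SAP 6.2 covers efficacy assessments after randomization at regular, early-termination and unscheduled visits, and states that "measurements from the visit within the visit window will be used for the analysis". Its table gives Days 87–97 for Visit 10 and Days 171–181 for Visit 16. For early-termination visits SAP 6.3 is stricter in wording: "analysis is performed as result of a regular visit only when it comes within the visit window corresponding to each regular visit".

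A footnote to the analysis-window column gives the only relief: "If a violation of the drug administration schedule occurs, the analysis window will be modified as the process in the protocol 5.5.2". Protocol 5.5.2 has two branches. For an injection given before its window (its example is −6 days), "the schedule will be adjusted by moving all subsequent administration days forward by one week". For a late visit, "If the window has passed, the corresponding drug administration will be skipped", and the next injection is given on the day originally scheduled.

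Protocol 10.3.12 schedules only two post-baseline PSP-ratings, at Visits 10 and 16. Dosing ends at Visit 15 (protocol 10.3.18). SAP section 12 plans no sensitivity analysis.

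**The concern.** Visits 10 and 16 are each 14 days from the visits on either side, and ±5-day windows cover only 11 of every 14 days. A rating taken in the remaining three days has no label, and no nearest-visit rule assigns one. The footnote deals with dosing days that come later, not with the visit that was mistimed.

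With 20 evaluable subjects planned per arm and one rating carrying the primary endpoint, each unused score costs precision. The missing value would come from the analysis rule, since the patient was seen and rated. If patients who are doing worse tend to attend late, which is plausible but not stated in the documents, the loss would also not be random. A subject rated on Day 182 could be in the FAS, and possibly the PPS, with no Week 24 value in the primary model. A FAS subject whose only post-dose rating lies in a gap would contribute nothing.

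**Working it through.** **1. Reproduce the plan's windows.** SAP 5.5 makes randomization Day 1 with no Day 0, so target day = 7 × (week − 1) + 1.
- Visit 10, Week 14: 7 × 13 + 1 = 92; ±5 gives 87–97.
- Visit 16, Week 26: 7 × 25 + 1 = 176; ±5 gives 171–181.
- Neighbours: Visit 9, 73–83; Visit 11, 101–111; Visit 15, 157–167; Visit 17, 185–195.

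All 15 post-baseline rows reproduce exactly.

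**2. Gaps.** Days in no window are 84–86 and 98–100 around Visit 10, and 168–170 and 182–184 around Visit 16. These are 6 to 8 days off target.

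**3. Apply the footnote.**
- Early Visit 10 injection, using the protocol's own example: 92 − 6 = Day 86. Only later dosing days move, so the Visit 10 window stays at 87–97 and the rating taken that day is outside it.
- Late Visit 10, say Day 98: the injection is skipped and no day moves. The rating is outside.
- Mistimed Visit 16, say Day 170 or 182: no injection is due, so no dosing violation triggers the footnote. The rating is outside.
- Early injection at a visit before Visit 10: the Visit 10 window moves a week. I read the shift as one to earlier dates, because the next biweekly dose then follows after 14 + 6 − 7 = 13 days; a shift to later dates would make it 14 + 6 + 7 = 27. Visit 10 becomes 80–90, and Visit 16, if it moves too, 164–174. The width is unchanged, so the same gaps remain.

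**4. Precision lost.** Inputs: n = 20 per arm (SAP 3.3). The number m lost per arm and the correlation r between the Visit 10 and Visit 16 changes are assumed, because the documents give neither. With Visit 10 observed in everyone and losses at random, the standard error ratio = √(20 × [(1 − r²)/(20 − m) + r²/20]).

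| m of 20 lost per arm | r = 0 (nothing recovered) | r = 0.5 | r = 0.7 |
|---|---|---|---|
| 1 | +2.6% | +2.0% | +1.3% |
| 2 | +5.4% | +4.1% | +2.8% |
| 4 | +11.8% | +9.0% | +6.2% |

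**5. Timing error from keeping them.** Protocol 3.3 cites a mean worsening of 6.8 points over 6 months in an earlier Phase 2/3 trial of another drug. Assumed linear over 26 weeks, that is 6.8 / (26 × 7) = 0.0374 points per day.
- 6 days off: 0.22 points; 8 days off: 0.30 points, for the affected subject.
- Worst case on an arm mean, 4 of 20 all 8 days off on the same side in one arm only: 4/20 × 0.299 = 0.060 points.
- Largest spread of rating days under one label: 10 days now (0.37 points), 16 days with ±8 (0.60 points).

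**6. Compare the two.** For an assumed SD of 6 to 10, the standard error of the difference with 20 per arm is 6 × √(2/20) = 1.90 to 10 × √(2/20) = 3.16. With m = 4:
- Keep, worst-case shift included: root mean square error √(1.897² + 0.060²) = 1.898 (SD 6) and 3.163 (SD 10).
- Drop, r = 0.7: 1.897 × 1.062 = 2.015 and 3.162 × 1.062 = 3.358.

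Of the correlations tabulated, r = 0.7 is the one most favourable to dropping.

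**7. Last-dose-to-rating interval.** With Visit 15 given on Days 157–167, the interval to a usable Visit 16 rating now runs from 171 − 167 = 4 to 181 − 157 = 24 days. With 168–184 it runs from 1 to 27 days.

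**The case against.** The strongest objection concerns how the gaps are repaired. The footnote's asterisk sits on the heading of the whole analysis-window column and makes no exception for visits without dosing. A reader might infer from protocol 5.5.2, which speaks only of administration days, that the Visit 16 window never moves. The documents do not settle this, and writing that reading into the SAP could lose data. Suppose one early injection at Visit 12 moves Visit 15 from Day 162 to Day 155, and the site keeps two weeks to Visit 16. The target becomes Day 169. A moved ±5-day window (164–174) keeps ratings on Days 164–167; a fixed window of 168–184 drops them. After two shifts the target is Day 162, and the whole range 157–167 would fall outside a fixed window. This stands in full: the wider windows must move with the schedule.

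A second inference to resist is that SAP 6.2 contradicts the rest of the plan. FAS entry requires that a subject "had at least 1 evaluation with the PSP-rating scale after the administration of the investigational product", with no window, but that decides who is analysed, not which values are used. The sentence that "the available data will be analyzed as they are since the method does not require the replacement of missing values" is about not imputing. Protocol 5.5.3 says minor violations "will be included in the per-protocol set analysis by accurately describing the extent of violation or delay and the reason", which governs PPS membership. None of these promises that every rating enters the model.

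Three further points stand.
- For regular visits, exclusion is the plain reading of 6.2. The explicit restriction appears only in 6.3, for early termination.
- Step 6 prices natural drift only and contains no term for the wider dose-to-rating interval in step 7.
- Days 85 and 169 are exactly 12 and 24 weeks after Day 1 and lie in the gaps, but the visits are scheduled for Days 92 and 176, so on-schedule ratings are not lost.

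Finally, a prespecified window equal to the conduct window is a defensible choice in an exploratory trial, and sites must remind subjects of their visits. That limits the weight of the point but leaves the gaps in place.

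**Conclusion.** The point holds as a cheap improvement. On the plain reading of SAP 6.2, ratings on Days 84–86, 98–100, 168–170 and 182–184 are assigned to no visit, and the footnote does not rescue the visit that was itself mistimed. If 1 to 4 of 20 Visit 16 ratings per arm fell there, the standard error would rise by about 1% to 12%. That range rests on assumed frequencies and correlations. In the m = 4 comparison the drift cost of keeping the ratings is small beside the precision recovered, given linear progression and an SD of 6 to 10. A reader might infer that the primary analysis is in danger; nothing in the documents shows that visits often miss ±5 days, so that is not supported.

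**What to change.** Change SAP 6.2 before unblinding.
- For the efficacy scales, set the analysis windows of Visits 10 and 16 to ±8 days: Days 84–100 and 168–184. This fills the gaps and overlaps no neighbouring window in the table.
- Keep ±5 days as the visit window for conduct.
- State that, if an early injection shifts a subject's later schedule, the ±8-day windows of Visits 10 and 16 move with that shifted schedule. After one shift, Visit 16 would be 169 ± 8 = Days 161–177. Do not add a sentence exempting Visits 16 and 17 from the footnote.
- Leave SAP 6.4 as it is: the regular-visit value is preferred when two fall in one window.

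The edit is two table rows and a sentence. It needs no protocol amendment, no extra visit and no change to dosing. The price is the wider spread of rating days (10 to 16) and of last-dose-to-rating intervals pooled at Visit 16 (4–24 to 1–27 days). Ratings more than 8 days off target, including many early-termination ratings, would still not count as Visit 10 or Visit 16 values.
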